To compare adult cochlear implant speech perception in spatially separated speech and noise (AuSTIN, 65 dB SPL SON3 Babble) between CP1170 microphone directionalities, SCAN 2 FF Zoom (Automated ForwardFocus ON) and SCAN 2 FF Beam (Automated ForwardFocus ON).	Paired difference in dB SRT (AuSTIN, 65 dB SPL SON3 Babble) between the CP1170 SCAN 2 FF Zoom (Automated ForwardFocus ON) and CP1170 SCAN 2 FF Beam (Automated ForwardFocus ON).
To compare subjective acceptance and satisfaction between microphone directionalities: CP1170 sound processor using SCAN 2 FF Zoom and CP1170 sound processor using SCAN 2 FF Beam.	Ratings based on the CP1170 Questionnaire after a minimum 2-weeks actual-use of the CP1170 sound processor SCAN 2 FF Zoom and CP1170 sound processor SCAN 2 FF Beam.

3 Schedule of Events

Visit Type	Screening	Visit 1 ^a	Visit 2 ^b	Ad Hoc ^c	EOS ^d
Timing of Investigation	Day 0	Day 0	Week 2	NA	Month 12
Visit window (±)	NA	+ 7 days	+ 14 days	NA	± 30 days
Written informed consent	X				
Demographics	X				
Eligibility	X				
Hearing history	X				
Device history	X				
Medical history	X				
Baseline Questionnaire ^e		X			
SSQ12 - Own Processor ^f		X			
SSQ12 - CP1170 Sound Processor ^g				X	
APHAB Questionnaire				X	
CP1170 Fitting ^h		X		X	
Fitting optimisation ⁱ			X	X	
Speech perception testing - Speech in Noise ^{jk}				X	
Speech perception testing – Words in Quiet ^l				X	

^a Screening and visit 1 may occur on the same day.

^b Visit 2 signifies the end of the first take-home period. Procedures from Ad Hoc visits may be performed on the same day as required.

^c Ad Hoc refers to any unscheduled visit and may be repeated.

^d EOS can occur on the same day as an Ad Hoc visit.

^e Information regarding the subject's own sound processor, i.e. that which they had been using prior to screening, and usage habits.

^f Own processor is defined as the sound processor that the subject used for a minimum of 2 weeks prior to their enrolment.

^g SSQ12 on the IMD following the final take-home period.

^h First fitting of the investigational sound processor.

ⁱ Fitting optimisation is subject to need and may include programming changes, and hardware or firmware modifications or updates to the investigational sound processor.

^j In-booth testing CP1170 SCAN 2 ForwardFocus ON compared with the CP1170 ForwardFocus OFF (65 dB SPL S0Nrearhalf 4-talker babble).

^k CP1170 ForwardFocus ON (SCAN 2) and ForwardFocus OFF (SCAN 2) (65 dB SPL S0N3 babble).

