Speech perception with babble noise from the rear demonstrated that ForwardFocus ON was superior to ForwardFocus OFF (Nucleus 7 default program, SCAN). Listening effort as measured via a dual-task paradigm involving both speech perception and a visual reaction time task revealed no significant difference in reaction times between ForwardFocus ON and ForwardFocus OFF, and therefore no difference in listening effort.

Questions from the Speech domain of the 'SSQ of Hearing Scale' and 3 questions from the 'Qualities of Hearing' domain were completed by subjects at baseline and after at least 4 weeks of use with ForwardFocus. The mean Speech domain results collected after 4 weeks of use were not significantly different from baseline scores.

Subjective ratings on the custom questionnaires indicated strong satisfaction, ease of use, and confidence with ForwardFocus. The majority of respondents found the ForwardFocus controls within the Nucleus Smart App as very easy to use and half of the respondents wanted ForwardFocus on their own processor.

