7.3.2.6 Subjective Ratings

7.3.2.6.1 Speech, Spatial and Qualities of Hearing Scale (SSQ12)

The SSQ is designed to measure a range of hearing disabilities across several domains. Subjects are asked to rate their ability to hear speech in a variety of competing contexts, subjects are also asked about their spatial hearing abilities including the impact of direction, distance and movement associated with spatial hearing. Subjects are also asked about their ease of listening, and the naturalness, clarity and identifiability of different speakers (Gatehouse & Noble, 2004; Noble, Jensen, Naylor, Bhullar, & Akeroyd, 2013). A shortened form of the 49-question SSQ, the SSQ12, will be used in this study.

Study subjects will be asked to complete the SSQ12 at two time points in the study; 1) at study entry, where scores will reflect their experience with their own sound processor, 2) after take home use with the Kanso 3 Sound Processor.

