9.2.2 Secondary Endpoints

1. Paired difference in dB SRT (AuSTIN) between the CP1170 SCAN 2 FF (Automated ForwardFocus ON) and CP1170 SCAN 2 (ForwardFocus OFF) in 65 dB SPL SON3 babble.
2. Paired difference in percentage CNC Words correct in quiet (50 dB) with the CP1170 sound processor and CP1150 sound processor.
3. Ratings based on the CP1170 Questionnaire after a minimum 2-weeks actual-use of the CP1170 sound processor in the home environment and the subject's own processor (Baseline Questionnaire).
4. Paired difference in Global SSQ12 scores after experience with the CP1170 sound processor and own processor (baseline).

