9.3.2 Secondary Hypotheses

Endpoint 1: Paired difference in dB SRT (AuSTIN) between CP1170 sound processor programs, SCAN 2 FF (Automated ForwardFocus ON) and SCAN 2 (ForwardFocus OFF). in 65 dB SPL SON3 babble. A non-inferiority margin of 1 dB is chosen based on clinical consensus.

H_0 : Sentence in noise (SON3) scores (dB SRT) with the Kanso 3 with SCAN 2 FF (treatment) are inferior to those with the Kanso 3 with SCAN 2

$Kanso\ 3\ SCAN\ 2\ FF\ ON - Kanso\ 3\ SCAN\ 2\ (ForwardFocus\ OFF) \geq 1\ dB$ (*NB: higher SRT scores represent poorer performance*)

H_1 : Sentence in noise (SON3scores (dB SRT) with the Kanso 3 with SCAN 2 FF ON (treatment) are inferior to those with the Kanso 3 with SCAN 2 (ForwardFocus OFF)

Kanso 3 SCAN 2 FF ON – Kanso 3 SCAN 2 (ForwardFocus OFF) < 1 dB

Endpoint 2: Paired difference in percentage CNC Words correct in quiet (50 dB) with the with the CP1170 sound processor (presented as Kanso 3 in the hypotheses) and the CP1150 sound processor (presented as Kanso 2 in the hypotheses). A non-inferiority margin of -10% is chosen based on clinical consensus.

H_0 : Words in quiet (50 dB CNC words) scores (% words correct) with the Kanso 3 (treatment) are inferior to those with the Kanso 2.

$CP1170 \text{ (Kanso 3)} - CP1150 \text{ (Kanso 2)} \leq -10\% \text{ (NB: lower CNC words represent poorer performance)}$

H_1 : Words in quiet (50 dB CNC words) scores (% words correct) with the Kanso 3 (treatment) are non-inferior to those with the Kanso 2.

$CP1170 \text{ (Kanso 3)} - CP1150 \text{ (Kanso 2)} > -10\%$

Endpoint 3: Paired difference in Global SSQ12 scores after experience with the Kanso 3. CP1170 Sound Processor (presented as Kanso 3 in the hypotheses) compared with the subject's own processor. A non-inferiority margin of -1 is chosen based on clinical consensus.

H_0 : Hearing performance ratings (SSQ12) with the CP1110 Sound Processor (treatment) are inferior to those with subject's own processor (control)

$Kanso 3 - \text{Own Processor} \leq -1 \text{ (NB: lower scores represent poorer performance)}$

H_1 : Hearing performance ratings (SSQ12) with the CP1110 Sound Processor (treatment) are non-inferior to those with subject's own processor (control)

$Kanso 3 - \text{Own Processor} > -1$

No formal hypotheses are specified for the following secondary endpoint:

- Ratings on the CP1170 Questionnaire.

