9.6.2 Secondary Endpoint Analyses

As with the primary endpoint, the non-inferiority testing of the secondary endpoints will also be conducted in the PP analysis set. If non-inferiority is demonstrated, the testing will proceed a test of superiority in the IIT analysis set.

For the non-inferiority test of SRT sentence scores (Kanso 3 with SCAN 2 FF ON versus Kanso 3 with SCAN 2 (ForwardFocus OFF) in 65 dB SPL SON3), the 95% CI (alpha=0.025 one-sided) for the mean paired difference will be estimated. If the upper limit of the 95% CI of the mean paired difference is below 1 dB, the treatment condition is regarded as non-inferior to the control in terms of SRT sentence perception. The non-inferiority margin of 1 dB for SRT is based on clinical consensus.

For the non-inferiority test of CNC words in quiet scores (monosyllables), the 95% CI (alpha=0.025 one-sided) for the mean paired difference will be estimated. If the lower limit of the 95% CI of the mean paired difference is above -10%, the treatment condition is regarded as non-inferior to the control in terms of words in quiet perception. The non-inferiority margin of -10% for words in quiet scores (monosyllables) is also based on clinical consensus.

For the non-inferiority test of Global SSQ12 scores, the 95% CI (alpha=0.025 one-sided) for the mean paired difference will be estimated. If the lower limit of the 95% CI of the mean paired difference is above -1, the treatment condition is regarded as non-inferior to the control.

Data from the other questionnaires including the results for individual questions on the SSQ will be summarised descriptively. Qualitative data will be summarised as appropriate.

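### Section 9.6.2 takes Global SSQ12 on to a superiority test, but the open-label, own-processor-first design cannot attribute a gain to the CP1170

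*Combined protocol and SAP*

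**What the plan says.** Section 9.6.2 opens with a rule for all secondary endpoints: non-inferiority is tested in the Per Protocol set, and then "If non-inferiority is demonstrated, the testing will proceed a test of superiority in the IIT analysis set" (IIT is evidently a misprint for ITT). The same section later makes SSQ12 one of three endpoints that get such a test: "For the non-inferiority test of Global SSQ12 scores, the 95% CI (alpha=0.025 one-sided) for the mean paired difference will be estimated". Section 9.3.2 supplies the margin: "A non-inferiority margin of -1 is chosen based on clinical consensus". The hypotheses written there for SSQ12 concern non-inferiority only. No superiority hypothesis or decision rule specific to SSQ12 appears anywhere.

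On how the ratings arise:

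- Section 7.3.2.6.1 has two time points. The first is "at study entry, where scores will reflect their experience with their own sound processor"; the second follows take-home use of the CP1170. Footnote g of the Schedule of Events (Section 3) puts the second rating after the final take-home period.
- Section 7.1 describes the study as open-label. Section 7.2.7.1 conceals test order for in-booth speech testing, and Section 7.2.7 counterbalances the primary and secondary speech perception endpoints. Neither covers SSQ12.
- Section 3, footnote i, says: "Fitting optimisation is subject to need and may include programming changes, and hardware or firmware modifications or updates to the investigational sound processor". Section 7.3.2.4 adds MAP adjustments and new features. No study optimisation of the own processor is described; Section 7.2.8 leaves subjects free to see their regular clinicians when wearing it.

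**The concern.** The superiority step suits the booth comparisons, where order is balanced and concealed from the subject. For SSQ12 the device contrast coincides exactly with the contrast between before and after. Anything that changes between study entry and the last take-home period enters the paired difference along with the processor: knowing that one is wearing a new device, having spent time in a study, and having had fitting attention that the own processor did not receive. Section 8.1 itself lists early access to new technology as a direct benefit to participants, so expectation is not far-fetched.

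A paired t-interval cannot separate these influences from a processor effect. At stake is one possible sentence in the report, that subjects rate their hearing as better with the CP1170 than with their own processor. The design cannot support that sentence as a statement about the device.

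**Working it through.** **1. Do the safeguards reach SSQ12?**

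| Feature | S0N3 SRT, CNC words | Global SSQ12 |
|---|---|---|
| Order | Counterbalanced (7.2.7) | Own processor always first (7.3.2.6.1) |
| Concealment from subject | Test order not revealed (7.2.7.1) | None described |
| Timing of the two measurements | Same day for each endpoint (7.3.4) | Study entry, then after the final take-home period |
| Superiority step | Yes (9.6.2) | Yes (9.6.2) |

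**2. Number of pairs, and a check of the plan's own figure.** Section 9.4 gives a margin of 1 dB, SD of the difference 1.36 dB, one-sided alpha 0.025 and power 0.8. The normal approximation is (1.36 × (1.960 + 0.842) / 1)² = 14.5, so 15. The exact paired calculation with the noncentral t gives power 0.785 at n=16 and 0.812 at n=17, so the stated 17 is reproduced; 17/0.85 = 20. SSQ12 would thus have about 17 to 20 pairs. Section 9.5 imputes nothing, so even in the ITT set only subjects with both ratings count.

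**3. Gain needed to declare superiority.** The lower 95% limit exceeds 0 when the mean difference exceeds t(0.975, n−1) × SD/√n. The documents give no SD for SSQ12, so 1.0 to 2.0 points is assumed.

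- n=17, t=2.120: 0.51 (SD 1.0), 0.77 (SD 1.5), 1.03 (SD 2.0).
- n=20, t=2.093: 0.47, 0.70, 0.94.

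**4. Sensitivity to a shift not caused by the processor.** Suppose the true processor effect is 0 and the mean difference is shifted upward by b. Taking PP and ITT as the same subjects, a lower limit above 0 has already passed the −1 margin, so

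P(superiority) = 1 − F(t(0.975, n−1); n−1 df, noncentrality b√n/SD),

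where F is the noncentral t distribution function. For example, n=17, b=0.5 and SD=1.0 give noncentrality 0.5 × 4.123 = 2.06 and probability 49.1%.

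| n | SD | b = 0 | b = 0.25 | b = 0.5 |
|---|---|---|---|---|
| 17 | 1.0 | 2.5% | 16.1% | 49.1% |
| 17 | 1.5 | 2.5% | 9.5% | 25.2% |
| 17 | 2.0 | 2.5% | 7.0% | 16.1% |
| 20 | 1.0 | 2.5% | 18.5% | 56.4% |
| 20 | 1.5 | 2.5% | 10.5% | 29.3% |
| 20 | 2.0 | 2.5% | 7.7% | 18.5% |

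**5. Non-inferiority.** Only the distance from the tested value enters the formula. If the true effect were exactly −1, the same shift would produce false non-inferiority with the same probabilities. The difference between the two claims is this: if the processors are in truth equal, an upward shift leaves a non-inferiority conclusion correct but makes a superiority conclusion wrong.

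**The case against.** The strongest reply is that no upward bias has been shown. The CP1170 starts from the subject's own maps (7.3.2.3), and optimisation is optional (7.3.2.4). Subjects are experienced users whose own device is under regular clinical care. The CP1170 may be rated after as little as two weeks, on early product that Section 7.3.2.5 expects may have issues, and Section 8.3 names reduced sound quality or intelligibility as a risk. Some of these could lower the CP1170 score. This stands: the direction is open, and re-fitting may not touch every subject. Fixed order and open-label rating do apply to all.

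A reader might go further and infer from Section 4.2.2.1 that a significant gain would more probably be bias than benefit, since of an earlier ForwardFocus study it says: "The mean Speech domain results collected after 4 weeks of use were not significantly different from baseline scores". The documents do not support that. The earlier result concerns one feature on a Nucleus 7 processor and the Speech domain of the SSQ. Here a whole new processor is compared, on the global SSQ12, with whatever processor the subject brought to the study. That earlier study also used a baseline-then-later rating and reported no significant shift, so it gives no support for an upward bias either.

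It can also be said that the percentages only restate assumed shifts, and that the test keeps its 2.5% level for the quantity defined in Section 9.3, the mean difference. Both are fair. The fault is one of attribution to the device, and the figures show sensitivity only.

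Finally, a reported CI lying above zero would show the same thing without the label. True, but what the trial formally concludes would change, and the limitation would be printed beside the interval.

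**Conclusion.** The point holds as one of attribution. Section 9.6.2 provides a superiority test for SSQ12, and the design gives that endpoint none of the protection that the speech endpoints have. A positive result could reflect the processor, expectation, time in study or re-fitting, and the analysis could not tell which.

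The size is unknown. Under an assumed SD of 1.0 to 2.0 and no true effect, a 0.25-point upward shift yields superiority in 7-16% of trials at n=17 (8-19% at n=20), and a 0.5-point shift in 16-49% (19-56%). These are not estimates of this trial's error rate. A reader might infer from them that the SSQ12 result will be biased upward, or that its non-inferiority test is invalid; the documents establish neither. The consequence is confined to one secondary endpoint. The primary endpoint and the speech secondary endpoints are untouched.

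**What to change.** In Section 9.6.2, limit the superiority step to the two counterbalanced speech endpoints, S0N3 SRT and CNC words. For Global SSQ12, report the planned non-inferiority result and the 95% CI and make no superiority claim. State that both are open-label, fixed-order before-after comparisons, and that the same influences could also favour non-inferiority.

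The cost is wording, plus the loss of a formal SSQ12 superiority claim. Section 9.1 allows departures from the planned analyses to be set out in the SAP, which under Section 14.3 must be final for database lock. Changing Section 9.6.2 itself would follow the amendment route in Section 18. SSQ12 is not among the interim analyses in Section 9.8, so the change can precede its analysis. The misprint IIT, and CP1110 in the SSQ12 hypotheses of Section 9.3.2, can be corrected at the same time; the point depends on neither.

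Two other remedies may come to mind and are not recommended. Repeating the own-processor SSQ12 late in the study as a new control would change the comparator defined in Section 9.2.2, invite contrast effects after CP1170 use, and need an amendment after recruitment was complete (Section 25). Leaving out subjects whose MAPs were adjusted would select on a need-driven event after baseline, in a sample of at most 20.

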9.6.3 Exploratory Endpoint Analysis

Descriptive summaries on subject compliance with the EMA mobile application and their responses will be presented. Compliance will be analysed according to how many times the subject completed or partially completed the real-time questionnaire as prescribed. Historical data, exported by the app, may be searched and summarised according to patterns in the subjective responses. Qualitative results will be summarised in the report.

There are no formal hypotheses planned for the exploratory endpoints relating to the investigation of speech perception (AuSTIN) in noise between CP1170 microphone directionalities, SCAN 2 FF (Automated ForwardFocus ON) with Zoom and SCAN 2 FF with Beam (Automated ForwardFocus ON) under the two different noise conditions, 65 dB SPL S0Nrearhalf 4TB and 65 dB SPL S0N3 Babble. These comparisons will be presented descriptively together with 95% interval estimates for the mean paired differences. No inferences will be made.

9.7 Safety Analyses

For AE/ADEs and DDs, the percentage of subjects who experienced at least one event related to the IMD will be summarised. Any subjects who died, who discontinued an intervention due to an AE/ADEs, or who experienced a severe or an SAE/SADEs will be summarised separately.

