7 DESIGN OF THE CLINICAL INVESTIGATION

7.1 General

This is a pre-market, prospective, single-site, open-label, within-subject, interventional study of acceptance and performance of the Kanso 3 Sound Processor (Model: CP1170) through actual-use with adult cochlear implant recipients. The IMD is the Kanso 3 Sound Processor, used in conjunction with the investigational version of Custom Sound Pro fitting software, investigational version of Nucleus Smart App. The comparators include acute use of the Kanso 2 Sound Processor (Model: CP1150) to compare performance in quiet and subject's own sound processor (i.e. any BTE or OTE which they entered the study with) to compare subjective performance and acceptance.

The subjects include adults aged 18 years and older who are currently using a Cochlear hearing implant. Subjects will be screened and 20 eligible subjects will be recruited in the clinical investigation from a single investigational site located in Australia. After enrolment, subjects will attend scheduled study visits for a period up to 12 months as described in the CIP Schedule of Events (Section 3). At study visits, subjects will undergo hearing assessments. Safety will be assessed by recording and summarising all Adverse Events (AE)/ Adverse Device Effects (ADE) and Device Deficiencies (DD). No data monitoring committee will be used for this clinical investigation. All subjects will attend an end-of-study visit at the time they complete the study.

The primary endpoint is to determine the hearing performance of the Kanso 3 Sound Processor with the new implementation of ForwardFocus in SCAN 2 (SCAN 2 FF), as assessed by speech perception in noise. Safety will be assessed by recording and summarising all AEs/ADEs and DDs. No data monitoring committee will be used for this clinical investigation. All subjects will attend an End-of-Study visit at the time they complete the study.

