9 STATISTICAL CONSIDERATIONS

9.1 General Considerations

Continuous data will be summarised by the number of non-missing observations, the mean, median, the standard deviation, and the minimum and maximum values. Categorical data will be summarised by the number and percentage of subjects in each category. Confidence intervals will be two-sided and at the 95% confidence level. For the primary and secondary endpoints, these will be t-distribution based confidence intervals; normality of the data will be assessed.

All demographic and baseline characteristics collected on the subjects will be summarised. Subject disposition including reasons for withdrawal will also be summarised. All subject data will be included in subject data listings.

No adjustment of the significance level will be made for multiplicity of testing.

Missing data will not be imputed.

Should any deviations to the analyses outlined in this section arise, these deviations will be detailed in the statistical analysis plan.

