11 ADVERSE EVENTS AND DEVICE DEFICIENCIES

11.1 Definitions

11.1.1 Adverse Event

An adverse event (AE) is any untoward medical occurrence, unintended disease or injury, or untoward clinical signs (including abnormal laboratory findings) in subjects, users or other persons whether or not related to the medical device or the procedures required for implant or use, and whether anticipated or unanticipated.

NOTE 1: This definition includes events related to the medical device or the comparator device.

NOTE 2: This definition includes events related to the procedures involved.

NOTE 3: For users and other persons, this definition is restricted to events related to the use of medical devices.

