11.1.7 Device Deficiency

A Device Deficiency (DD) is an inadequacy of a medical device with respect to its identity, quality, durability, reliability, usability, safety, or performance.

NOTE 1: Device Deficiencies include malfunctions, use errors, and inadequacy in the information supplied by the manufacturer including labelling.

NOTE 2: This definition includes device deficiencies related to the IMD or the comparator.

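### Section 9.7 plans the general AE/ADE and DD incidence summary for IMD-related events, which is narrower than the summary of all AEs/ADEs and DDs stated in Section 7.1

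*Combined protocol and SAP*

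**What the plan says.** Section 7.1 (General) states the scope of the safety assessment twice, in nearly the same words. One version reads "Safety will be assessed by recording and summarising all AEs/ADEs and DDs". Neither version restricts the scope by relatedness.

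Section 9.7 (Safety Analyses) is the only section that specifies how safety data are analysed. Its first sentence covers AE/ADEs and DDs and says that "the percentage of subjects who experienced at least one event related to the IMD will be summarised". Its second sentence takes subjects who died, those who discontinued because of an AE/ADE, "or who experienced a severe or an SAE/SADEs will be summarised separately". That second sentence has no relatedness condition.

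The definitions in Section 11.1 are broad. An AE counts "whether or not related to the medical device or the procedures required for implant or use". Section 11.1.2 defines an ADE as a device-related AE and, in Note 3, brings in a comparator that is a medical device. For DDs, Section 11.1.7 adds: "This definition includes device deficiencies related to the IMD or the comparator". Sections 11.2 and 11.4 require all AEs to be recorded and all AEs and DDs to be entered in the eCRF.

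Section 9.1 adds two general rules. On listings: "All subject data will be included in subject data listings". On the SAP: "Should any deviations to the analyses outlined in this section arise, these deviations will be detailed in the statistical analysis plan".

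**The concern.** A reader of Section 7.1 expects a table of all AEs and all DDs. A programmer working from Section 9.7 would produce a table of IMD-related events plus the separate serious and severe categories. The two outputs differ, and collection is not the cause, because unrelated AEs and comparator deficiencies are both captured.

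At stake is how far the safety table depends on a causality call. A moderate, non-serious AE that did not stop device use is tabulated if it is judged IMD-related and otherwise is not. Investigators make that call. They are unblinded (Section 7.1.1) and employed by the sponsor (Section 7.5), and the sponsor adjudicates safety data (Section 7.3.3) and reviews causality (Section 11.4.2). An all-AE line does not depend on that judgement, which is the usual reason for reporting one beside the related events.

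**Working it through.** No arithmetic applies. The check compares the stated scopes and asks which events Section 9.7 leaves without a summary.

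**Step 1: what is collected.** All AEs whatever their relatedness, and DDs of the IMD or a comparator (Sections 11.1.1, 11.1.7, 11.2, 11.4).

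**Step 2: what Section 7.1 says will be summarised.** All AEs/ADEs and DDs. This matches Step 1.

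**Step 3: what Section 9.7 specifies.** Each kind of event, set against the two sentences of 9.7:

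| Event | Sentence 1 (IMD-related) | Sentence 2 (separate summaries) | Specified output |
|---|---|---|---|
| AE judged IMD-related | Yes | If fatal, severe, serious or a cause of discontinuation | Summary |
| AE not judged IMD-related, but fatal, severe, serious or a cause of discontinuation | No | Yes | Summary |
| AE not judged IMD-related, mild or moderate, non-serious, not a cause of discontinuation (including a comparator-related ADE) | No | No | Listing |
| DD of the IMD | Yes | Not applicable | Summary |
| DD of a comparator | No | No | Listing |

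The third and fifth rows are the gap between 9.7 and 7.1.

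**Step 4: the wording of 9.7 itself.** Under Section 11.1.2 an AE related to the IMD is already an ADE. Restricting AE/ADEs to IMD-related events therefore leaves no AE line distinct from the ADE line, although the sentence names both.

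**Step 5: the relatedness filter.** Section 11.2.2 has five causality grades: not, unlikely, possibly, probably and definitely related. Section 9.7 does not say which of them count as related. Section 11.2.2 also sends cases that cannot be assessed, or that lack information, to the possibly related grade. If that grade counts as related, the default moves uncertain cases into the summary and partly mitigates the dependence on judgement.

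**Step 6: which comparator.** The synopsis names CP1150. Section 7.1 also treats the subject's own processor as a comparator, and Section 7.2.8 has subjects return to it after test sessions and take-home periods. CP1150 use is acute, but use of the own processor is not, so the documents do not show whether comparator deficiencies will be few or many.

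**Step 7: size.** The plan has 20 subjects followed for up to 12 months and states no expected AE or DD rate. The number of subjects in the third and fifth rows cannot be calculated.

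**The case against.** The strongest reply is that 9.7 does not use the word only. It names one statistic and some separate summaries and forbids nothing. Section 7.1 is part of the same plan, so an analyst could produce the 9.7 statistic and an all-AE summary and comply with both. Section 9.1 also has a general rule that categorical data are summarised by counts and percentages. This stands in part: a reader might infer that the two sections are incompatible, and they are not. Section 9.7 is narrower than 7.1. But the general rule in 9.1 does not mention AEs, and nothing in 9.7 asks for the wider table.

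A second reply is that the SAP could add the table. A reader might infer from Section 9.1 that the SAP may hold nothing except deviations. The text does not say that; it says deviations will be detailed there, and Section 14.3 requires a final SAP before database lock. A later SAP could supply the summary, but nothing in the documents commits it to do so.

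A third reply concerns weight. Everything is recorded and listed, and with 20 subjects a tally from the listings is feasible. Safety is not among the listed objectives or endpoints, and Section 11.5 describes the study as low risk. On independence, Section 7.5 describes SOPs that separate investigator and sponsor activities, and Section 11.4.1 has the investigator report safety events to the ethics committee. All of this stands. It lowers the severity without closing the gap, because the plan treats a listing and a summary as different outputs.

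**Conclusion.** The point holds as a minor inconsistency in reporting scope. Read as written, 9.7 specifies less than 7.1 promises. The shortfall is non-IMD-related AEs that are mild or moderate, non-serious and not a cause of discontinuation, together with deficiencies of a comparator (CP1150 or, where treated as one, the subject's own processor). No data are lost, and no endpoint, alpha or sample size changes.

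Two further inferences should be resisted. Mild and moderate are two of the three severity grades in Section 11.2.1, but that counts labels and says nothing about the share of events or subjects affected. And although the relatedness judgement is not independent of the sponsor, the documents do not show that it will be biased; they show that entry to the table depends on it.

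The conclusion rests on two assumptions: that the first sentence of 9.7 would be programmed as it stands, and that no separate SAP text adds an all-AE and all-DD summary.

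**What to change.** Reword the first sentence of Section 9.7 so that, in the Safety Population, the number and percentage of subjects with at least one AE, and with at least one DD, are summarised regardless of relationship to the IMD, with IMD-related events shown as a subset. Keep the second sentence and its separate summaries of deaths, discontinuations, severe events and SAEs/SADEs.

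Optional additions, which Section 7.1 does not require, are event counts, a split of DDs by device (naming which comparator is meant), and a statement of which causality grades count as related.

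The cost is one sentence and one or two descriptive tables from data already in the eCRF. No new data item is needed, and no endpoint, alpha or sample size changes.
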